2.1 Primary objective

To document the long-term safety and tolerability profile of pasireotide s.c. when administered as monotherapy or in combination with other therapies in patients with Cushing's disease.

2.1.1 Endpoint for primary objective

Incidence of pasireotide s.c.-related adverse events and serious adverse events during the 3-year observation period

2.2 Secondary objectives

- To document the short and long-term efficacy of pasireotide s.c. as measured by the proportion of patients that reach mean UFC \leq ULN at 1, 3, 6, 12, 24 and 36 months after enrolling into the study
- To document the changes of biochemical measures of disease activity (mean UFC, serum cortisol, serum cortisol after dexamethasone testing, salivary cortisol, ACTH and fasting serum lipid profile) over time
- To document normalization of biochemical measures of disease activity (serum cortisol, serum cortisol after dexamethasone testing, salivary cortisol and ACTH) over time, where normalization refers to being within the upper and lower limit of normal ranges
- To document the changes of measures of clinical signs and symptoms (blood pressure, body weight, body mass index, waist circumference) over time
- To document the changes in clinical symptoms of Cushing's disease over time
- To document the changes in safety and efficacy parameters over a period of 3 months after discontinuing pasireotide s.c. treatment for patients that permanently discontinue pasireotide s.c. prior to completing 3-year observation period
- To document the changes in tumor size over time
- To document the changes in patient-reported outcome questionnaires (Cushing QoL and EURO QoL)
- To document the overall safety and tolerability of pasireotide s.c.

2.2.1 Endpoints for secondary objectives

- Proportion of patients with a mean UFC \leq ULN at 1, 3, 6, 12, 24 and 36 months after enrolling into the study
- The absolute and percentage change from baseline in biochemical measures of disease activity (mean UFC, serum cortisol, serum cortisol after dexamethasone testing, salivary cortisol, ACTH and fasting serum lipid profile) over time
- Proportion of patients achieving normalization of biochemical measures of disease activity (serum cortisol, serum cortisol after dexamethasone testing, salivary cortisol and ACTH) over time
- The absolute and percentage change from baseline in clinical signs and symptoms (blood pressure, body weight, body mass index, waist circumference) over time
- The proportion of patients with favorable shift from baseline in clinical symptoms of Cushing's disease over time
- The change from the last dose of pasireotide s.c. to 3 months after permanent discontinuation of pasireotide s.c. for patients that discontinue pasireotide s.c. prior to completing the 3-year observation period. This change will be evaluated for all available continuous safety and efficacy parameters
- The absolute and percentage change from baseline in tumor size over time
- The absolute and percentage change from baseline in patient -reported outcome questionnaires (Cushing QoL and EURO QoL) over time
- Incidence of Adverse events and assessments of vital signs, blood pressure, heart rate, body temperature, blood glucose (fasting plasma glucose, HemoglobinA1c), hormones (GH, IGF-I, TSH/free T4), liver enzymes (AST, ALT, alkaline phosphatase, γ GT, total bilirubin), hematology, electrolytes, immunological events (e.g., allergic reactions: rash, pruritus, injection site reactions), gallbladder ultrasound and ECGs assessment values

3 Investigational plan

3.1 Overall study design

This is a non-interventional, multinational, multi-center post-marketing study, to further document the safety and efficacy of pasireotide s.c. administered in routine clinical practice in patients with Cushing's disease.

Patients with Cushing's disease and treated with pasireotide s.c. alone and in combination with other therapies will be monitored. For this study, each enrolled patient will be followed up for 3 years after enrollment. Patients who permanently discontinue pasireotide s.c. prior to completing the 3-year observation period will be followed up for 3 months after the last dose of pasireotide s.c.

3.1.1 Safety and tolerability assessments

All safety assessments will be collected from patient's enrollment into the study by signing the informed consent or acknowledging an equivalent document (e.g., written information) as per country regulation until the last dose of pasireotide s.c. at the patient's last follow-up visit within the 3 year observation period or until 3 months after the last dose for patients who permanently discontinue pasireotide s.c. prior to completing 3-year observation period.

- Adverse events and Serious Adverse Events will be followed-up and collected from patient's enrollment into the study until 28 days after the last dose of pasireotide s.c. at the patient's last follow-up visit. Adverse events and Serious Adverse Events will be collected until 3 months after the last dose for patients who permanently discontinue pasireotide s.c. prior to completing 3-year observation period.
- Special safety assessments will be collected from patient's enrollment into the study until the last follow-up visit as available or until 3 months after the last dose for all available safety parameters, for patients who permanently discontinue pasireotide s.c. prior to completing the 3-year observation period. Safety data to be collected include: vital signs, blood pressure, heart rate, body temperature, blood glucose (fasting plasma glucose, HemoglobinA1c), hormones (IGF-1, GH, TSH/free T₄), liver enzymes (AST, ALT, alkaline phosphatase, γGT, total bilirubin), hematology, electrolytes, immunological events (e.g., allergic reactions: rash, pruritus, injection site reactions), gallbladder ultrasound and ECGs.
- Medical history including history of smoking, history of alcohol use, presence of hepatitis B and C infection will be recorded at patient's entry in the study. Prior/concomitant medications/significant non-drug therapies (e.g., surgery, radiation) will be collected from patient's enrollment into this study until the last follow-up visit as available or until 3 months after the last dose for patients who permanently discontinue pasireotide s.c. prior to completing the 3-year observation period.

3.1.2 Efficacy assessments

All efficacy assessments will be collected from patient's enrollment into this study until the last follow-up visit for patients who complete the 3-year observation period or until 3 months after the last dose for patients who permanently discontinue pasireotide s.c. prior to completing the 3-year observation period.

- Urinary Free Cortisol (UFC). In general UFC is determined by collecting two or three 24-hour urine samples and calculating the mean. However routine site procedures may also only foresee one single urine sample to assess UFC. The frequency of UFC determination will probably vary from the initiation of treatment (when UFC values will be performed more frequently than at monthly interval) as compared to the time after obtaining control.
- Biochemical measures of disease activity: serum cortisol, serum cortisol after dexamethasone testing, salivary cortisol, plasma ACTH and fasting serum lipid profile.
- Measures of clinical signs and symptoms: Blood pressure, body weight, body mass index, waist circumference, clinical symptoms of Cushing's disease.
- Changes in tumor size as measured by MRI or other imaging techniques
- Changes in the quality of life score determined from a patient reported quality of life questionnaire (Cushing QoL and EURO QoL).

3.2 Discussion of design

This is a non-interventional, multinational, multi-center post-marketing study, to further document the safety/tolerability and efficacy of pasireotide s.c. in patients with Cushing's disease.

This study is observational in nature and does not impose a therapy protocol, diagnostic/therapeutic interventions or a visit schedule. Patients with Cushing's disease who are treated with pasireotide s.c. will be followed up for 3 years from patient's enrollment into this study, unless the patient discontinues pasireotide s.c. prematurely. If patients discontinue pasireotide s.c. prior to completing the 3 year observation period then any available safety and efficacy parameter will be collected until 3 months after the last dose of pasireotide s.c.

The timeframe of 3 years will allow to investigate the long-term safety/tolerability and efficacy of pasireotide s.c. including important safety evaluation on pasireotide s.c.-induced glycaemia effects, as well as the long-term changes of pituitary hormones and their by-products. The 3 year observation period is long enough to allow for the stabilization of the biochemical measures of disease activity (i.e. UFC and plasma ACTH), thus reducing the confounding effect of acute changes in UFC on the long-term safety measures (such as glycaemia, and pituitary hormones).

3.3 Study population

3.3.1 Patient population

The patient population will consist of male and female patients aged 18 years or older with a diagnosis of Cushing's disease for whom surgery has failed or for whom surgery is not an option and who are treated with pasireotide s.c. Investigators need to ensure that patients enrolled in this study meet the inclusion and exclusion criteria described in [Section 3.3.1.1](#).

Approximately 100 sites in about 35 countries will participate in this study.

The study will enroll a minimum of 100 patients to a maximum of 200 patients. Recruitment is expected to take approximately 96 months. The actual sample size may differ from this planned number.

Inclusion and exclusion criteria

3.3.1.1 Inclusion criteria

Patients eligible for inclusion in this study have to meet all of the following criteria:

- Written informed consent or equivalent document (e.g., written information) as per country regulation prior to registration of any patient data
- Male or female patients aged 18 years or older with a diagnosis of Cushing's disease for whom surgery has failed or for whom surgery is not an option
- Patients must be treated with pasireotide s.c. started either at the first visit for this study or prior to study entry

3.3.1.2 Exclusion criteria

- Patients with ectopic ACTH-dependent Cushing's syndrome

- Patients with adrenal Cushing's syndrome
- Patients with Pseudo Cushing's syndrome

3.4 Treatments

3.4.1 Pasireotide therapy

This observational study will include patients who are prescribed commercial pasireotide s.c. medication. The overall treatment pattern with pasireotide s.c. should be consistent with the local prescribing information.

3.4.1.1 Treatment discontinuation

Patients who permanently discontinue treatment with pasireotide s.c. prior to the 3-year observation period will have to be withdrawn from this study. Patients who discontinue pasireotide s.c. treatment because of an adverse event, must be followed by the investigator until resolution of the AE or until 3 months following discontinuation of drug whichever is longer.

All available safety and efficacy parameters will be collected for a period of 3 months following the last dose of pasireotide s.c. for patients who permanently discontinue pasireotide s.c. prior to completing the 3-year observation period.

Patients may voluntarily withdraw from this study or discontinued at the discretion of the investigator at any time. If such withdrawal occurs the investigator should determine the primary reason for a patient's premature withdrawal from this study. The withdrawal reason should be categorized into one of the following:

- Adverse event(s)
- Protocol deviation
- Subject withdrew consent or equivalent document (e.g., written information) as per country regulation
- Lost to follow-up
- Administrative problems
- Death
- Unsatisfactory therapeutic effect

For patients who are lost to follow-up, the investigator should show "due diligence", for the first 3 months after the last known date the patient took pasireotide, by documenting in the source documents steps taken to contact the patient, e.g. evidence of two certified letters, dates of telephone calls, sent emails.

3.4.1.2 Medical history and prior/concomitant treatment of Cushing's disease

Medical history of Cushing's disease including history of smoking, history of alcohol use, and presence of hepatitis B and C infections will be collected at patient's entry to the study. Prior/concomitant treatments and significant non-drug therapies for the management of Cushing's disease will also be collected as available when patients enroll into the study.

3.5 Visit schedule and assessments

This study is observational in nature and does not impose a therapy protocol, diagnostic/therapeutic interventions or a visit schedule. However, in order to help encourage more uniform data collection across study sites and patients a suggested schedule of assessments has been provided in [Table 3-1](#).

Patients will be treated with pasireotide s.c. according to the investigator's judgment and in accordance with the local (country-specific) pasireotide s.c. prescribing information. Available data will be collected at patients' visits to their site.

Table 3-1 Suggested schedule of assessments

Visit/Frequency	Baseline	Monthly	Every 3 months	Every 6 months	Every 12 months	End of Treatment	End Of study
Informed Consent	x						
Demography	x						
Inclusion/Exclusion Criteria	x						
Relevant medical history/Current medical conditions (history of smoking, history of alcohol use, presence of hepatitis B and C infections)	x						
Cushing's disease history	x						
Prior medications - For Cushing's Disease	x						
Coagulation test (Prothrombin time, APTT)	x					x	x
Vital Signs	x	x	x	x	x	x	x
Pregnancy test	x	x	x	x	x	x	x
Clinical symptoms of Cushing's disease	x		x			x	x
Glycemic status, FPG	x ¹	x ²				x ³	x ³
Glycemic status, HbA1c	x ¹		x			x ⁴	x ⁴
Salivary cortisol	x	x ⁵	x			x	x
Serum cortisol after dexamethasone	x	x ⁵	x			x	x
24 hour urine collection - Urinary free cortisol	x	x ⁵	x			x	x
Pituitary imaging local analysis (MRI/CT scan)	x				x	x	x
LFTs (ALT, AST, Alkaline phosphatase)	x ¹	x ⁶	x			x	x
12 lead ECG evaluation - local analysis	x ^{1,7}		x			x	x
Hematology/Blood Chemistry *	x			x		x	x
Thyroid function tests (TSH, Free T4)	x				x	x	x
Gallbladder imaging	x ¹			x	x	x	x
Cushing's syndrome QoL/ Euro QoL-5D health QoL/ Patient Reported outcome (PRO)	x			x		x	x

Visit/Frequency	Baseline	Monthly	Every 3 months	Every 6 months	Every 12 months	End of Treatment	End Of study
Dose Administration Record-Pasireotide s.c	x	At each visit				x	x
Adverse Events	x	At each visit				x	x
Concomitant Medication	x	At each visit				x	x

¹ prior starting treatment with pasireotide s.c
² self-monitoring of blood glucose and/or FPG every week for the 1st two to three months and periodically thereafter, as clinically appropriate.
³ Monitoring of FPG 4 weeks after the end of treatment
⁴ Monitoring of HbA1c 3 months after the end of treatment
⁵ every month for the first 3 month and then every 3 months
⁶ Monitoring of liver function after one, two, four, eight and twelve weeks
⁷ one week after start of treatment, QTcF/QTcB prolongations > 480 msec have to be reported as adverse events
* **Hematology:** WBC, RBC, Hemoglobin, Hematocrit, Platelets, Neutrophils, Lymphocytes, Eosinophils, Basophils, Monocytes
Blood chemistry: γGT, α-amylase, Total bilirubin, Indirect bilirubin, Direct bilirubin, Sodium, Potassium, Magnesium, GH, IGF-1, PT, Plasma ACTH, Triglyceride, Cholesterol, LDL, HDL

Recommended assessments are specified and listed in the local product label.

3.5.1 Patient demographics and other baseline characteristics

Standard demographic information (demography, vital signs) and medical history (including history of smoking, history of alcohol use, hepatitis B and C infection)/current medical conditions, concomitant medications and significant non-drug therapies will be collected as available.

3.5.2 Safety assessments

Safety assessments to be collected in this study will consist of all adverse events, including serious adverse events. Adverse events and Serious Adverse Events will be reported and collected from patient's enrollment into the study until 28 days after the last dose of pasireotide s.c. at the patient's last follow-up visit. Adverse events and Serious Adverse Events will be collected until 3 months after the last dose for patients who permanently discontinue pasireotide s.c. prior to completing 3 years of treatment.

3.5.2.1 Adverse events

Information about all adverse events including serious adverse events (SAEs), whether volunteered by the subject, discovered by investigator questioning, or detected through physical examination, laboratory test or other means, must be collected and recorded in the Adverse Event section of the study database (eCRF) irrespective of causal association. The investigator has to include information on all AEs in the individual patient eCRFs. The investigator has to commit to updating this information on a periodic basis but not later than once a month. Information on non-serious AEs is then transferred from the study database to Recordati by PPD data management on a periodic basis but not less frequently than once a month.

All AEs including SAEs occurring in association with exposure to another Recordati drug, if applicable, also have to be notified for recording in the Recordati safety database. Adverse reactions identified for non-Recordati products should be reported to the local Health Authority in accordance with national regulatory requirements for individual case safety reporting or the Marketing Authorization Holder; these will not be recorded in the Recordati safety database.

An adverse event is any undesirable sign, symptom or medical condition occurring on treatment with pasireotide s.c. even if the event is not considered to be related to pasireotide s.c. Medical conditions/diseases present before starting pasireotide s.c. treatment are only considered adverse events if they worsen after starting pasireotide s.c. Abnormal laboratory values or test results constitute adverse events only if they induce clinical signs or symptoms, are considered clinically significant or require therapy, and are recorded in the Adverse Events section. Adverse events will be collected after patients have signed the informed consent or acknowledged an equivalent document (e.g., written information) as per country regulation.

Adverse events will be assessed according to the Common Toxicity Criteria for Adverse Events (CTCAE) version 3.0. If CTCAE grading does not exist for an adverse event (document available upon request), the severity of mild, moderate, severe, and life-threatening, **or** grades 1 - 4, will be used.

In addition, all reports of the following special scenarios are also considered an adverse event irrespective if a clinical event has occurred:

- Drug-drug or drug-food interaction
- Drug use during lactation
- Lack of efficacy

Reports of lack of efficacy without an associated clinical event must be recorded on the AE CRF even if lack of efficacy parameters are being collected and recorded elsewhere within the study database.

- Overdose
- Intentional drug abuse and misuse
- Medication errors including drug maladministration
- Dispensing or prescribing errors

Reports of overdose, drug abuse and misuse, drug maladministration and dispensing errors/medication errors without an associated clinical event must be recorded on the AE CRF irrespective of whether or not the information is also being captured on the drug administration record form.

- Drug dependence or addiction
- Withdrawal reaction/syndrome or rebound symptoms
- Unexpected beneficial effect
- Treatment non-compliance (with clinical symptoms)

Note: Occupational or accidental exposure, for example of study personnel or family members of the patient should be reported to the local Health Authority in accordance with national regulatory requirements for individual case safety reporting or Recordati as a spontaneous report.

Any treatment of any adverse event should be recorded on the Adverse Event CRF. Some examples of treatment to be recorded are: no action taken (i.e., further observation only); drug of interest dosage adjusted/temporarily interrupted; drug of interest permanently discontinued due to this adverse event; treatment medication introduced or adjusted; non-drug therapy given; patient hospitalized/patient's hospitalization prolonged.

Once an adverse event is detected, it should be followed until its resolution or until it is judged to be permanent, and assessment should be made at each visit (or more frequently, if necessary) of any changes in severity, the suspected relationship to the drug of interest, the interventions required to treat it, and the outcome.

Information about common adverse effects already known about the medicinal product can be found in the locally available labeling document for the approved indication under evaluation in this study.

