### 4.1 Data analysis general information

Data will be summarized and displayed by time intervals based visit windows rather than by a strict visit schedule.

Patients who discontinue treatment prior to the 3-year observation period, will have their safety and efficacy parameters reported according to the time window that corresponds to Day of last dose of pasireotide s.c. plus 90 days.

Continuous variables will be summarized by number of patients, mean, standard deviation, minimum, median and maximum. Categorical variables will be summarized by absolute and relative frequencies. Counts of missing values for both continuous and categorical variables will be reported.

The study is exploratory in nature and no formal hypothesis testing is planned.

Data will be analyzed according to the data analysis Section 6 of the study protocol (as amended on 20SEP2013) which is available in Appendix 16.1.1 of the CSR. Details are given in the following sections and more technical details are provided, as applicable, in Appendix 16.1.9 of the CSR. It is planned that the data from all study sites that participate in this study will be pooled, so that an adequate number of patients will be available for analysis.

Interim analyses will be performed every year as requested by Health Authorities. The first analysis will be conducted about 12 months after the first patient enters the study. After this first analysis there will be one interim analysis on a yearly basis. The recruitment period is expected to be approximately 8 years and each enrolled patient will be followed up for 3 years after enrollment. The final analysis will occur when all patients have completed the study. The same analysis will be performed at all analysis time points.

For each analysis a cut-off date will be set. All data collected up to this cut-off date will be included in the analysis.

Any data collected beyond the cut-off date for an analysis will not be included in the analysis. Only data with an assessment date or event start date (e.g. vital sign assessment date or start date of an adverse event) prior to or on the cut-off date will be included in the analysis. For example, if the cut-off date is 15 June 2010 then an AE starting on 13 June 2010 will be reported, whereas an AE with start date on 17 June 2010 will not be reported.

---

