### 8.4.1 Adverse events (AEs)

All adverse events and the cause of death, as recorded on the completion CRF pages, will be coded using the latest version of the MedDRA coding dictionary that provides the system organ class (SOC) and preferred term (PT) information.

The number and percentage of patients reporting any AE will be summarized by primary SOC and PT. AEs and Serious Adverse Events (SAEs) will be reported and collected from patient's enrollment into the study until 28 days after the last dose of pasireotide s.c. at the patient's last follow-up visit. AEs and SAEs will be collected until 90 days after the last dose for patients who permanently discontinue pasireotide s.c. prior to completing 3 years of treatment.

The primary endpoint of this study is the percentage of patients having any pasireotide s.c.- related AEs and SAEs during the 3-year observation period. Pasireotide s.c.-related AEs are AEs for which the investigator suspected a relationship with pasireotide s.c.

AEs that started or worsened during the on-treatment period are called treatment-emergent AEs.

The incidence of treatment-emergent AEs will be summarized by system organ class (SOC), preferred term (PT) and severity. A patient with multiple occurrences of an AE will be counted only once in the respective AE category.

---

Study Code: CSOM230B2410

The following selection of treatment-emergent AEs will be listed and summarized, overall and by cohort:

- AEs regardless of relationship with pasireotide s.c. (additionally by country). This summary (> 5% in all patients) will also be prepared for the subgroup of patients from German sites
- AEs suspected to be related to pasireotide s.c.
- SAEs regardless of relationship with pasireotide s.c. (additionally by country)
- Deaths
- AEs leading to study drug discontinuation, regardless of relationship with pasireotide s.c. (restricted to patients with primary reason for discontinuation documented as AEs or abnormal laboratory values)
- AEs leading to study drug discontinuation, suspected to be related to pasireotide s.c. (restricted to patients with primary reason for discontinuation documented as AEs or abnormal laboratory values)
- AEs requiring dose adjustment or study-drug interruption, regardless of relationship with pasireotide s.c.
- AEs requiring additional therapy, regardless of relationship with pasireotide s.c.
- Adverse events of special interest, regardless of relationship with pasireotide s.c.

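### Special-scenario reports with no clinical event are AEs by definition, and the SAP neither separates them from the primary related-AE percentage nor from the AE tables

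*Protocol*

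**What the plan says.** Protocol 3.5.2.1 opens with a conventional definition: "An adverse event is any undesirable sign, symptom or medical condition occurring on treatment with pasireotide s.c". It then widens it, because "all reports of the following special scenarios are also considered an adverse event irrespective if a clinical event has occurred". The list covers interactions, use during lactation, lack of efficacy, overdose, abuse and misuse, medication errors, dispensing or prescribing errors, dependence, withdrawal or rebound, and "Unexpected beneficial effect". Only treatment non-compliance is limited to cases with clinical symptoms.

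Recording is mandatory. For lack of efficacy, "Reports of lack of efficacy without an associated clinical event must be recorded on the AE CRF". The same holds for overdose, misuse and maladministration, and "dispensing errors/medication errors without an associated clinical event must be recorded on the AE CRF". A beneficial effect gets no sentence of its own, but the section requires every AE to be entered in the eCRF. For each AE the investigator assesses "the suspected relationship to the drug of interest"; no guidance says how to do this for a special scenario.

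On the analysis side, SAP 8.4.1 says: "The primary endpoint of this study is the percentage of patients having any pasireotide". It completes the definition with drug-related AEs and SAEs over the three-year observation period, where related means that the investigator suspected a relationship. Protocol 6.4.1 and 6.5.2.1 match. SAP 8.4.1 also plans AE tables regardless of relationship and, using the method in SAP 6.2.4, exposure-adjusted rates by preferred term. None of these sections excludes, flags or separately tabulates special-scenario reports.

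**The concern.** The primary objective is to describe safety and tolerability. A patient-level percentage with any related AE should mean the share of patients in whom harm was suspected. As the counting rules stand, a patient whose only related record is lack of efficacy, or an unexpected benefit, counts the same as a patient with related hyperglycaemia. Rows by system organ class and preferred term can be inspected, but a reader of the report cannot recover the any-related-AE figure without these patients, because patients with several events are counted once.

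The AE definition also differs over calendar time. The amendment history dates the list to Amendment 2, 25 July 2016, while enrolment began in March 2013. The primary percentage pools both periods.

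**Working it through.** The plan gives no figure to reproduce: there is no expected AE rate, no hypothesis test (Protocol 6.4.2) and no statistical basis for the sample size (Protocol 6.7). The check therefore has two parts.

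**1. Which outputs a report without a clinical event can reach**

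- *Primary related-AE percentage (SAP 8.4.1).* The only filter is the investigator's suspected relationship. A report enters if it is marked as suspected, and not otherwise.
- *AE tables regardless of relationship (SAP 8.4.1).* There is no filter beyond on-treatment onset, so all such reports enter.
- *Exposure-adjusted AE rates (SAP 6.2.4, 8.4.1).* These count events by preferred term, regardless of relationship. Reports enter if the term has more than 2 occurrences.
- *SAEs (Protocol 3.5.2.2).* These still require an undesirable sign, symptom or condition that meets a seriousness criterion, so they are largely unaffected.
- *Discontinuation tables (SAP 8.4.1).* These are restricted to patients whose main reason for stopping was an AE or an abnormal laboratory value. Unsatisfactory effect is a separate withdrawal reason in Protocol 3.4.1.1, so these tables are largely unaffected.

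**2. How much the primary percentage could move**

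The three inputs are assumptions; the documents give none of them.

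- p: share of patients with a genuine related clinical AE
- q: share of the remaining patients who have only a special-scenario report
- r: share of those that the investigator marks as suspected related

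Counted percentage = p + (1 − p) × q × r, so the increase is (1 − p) × q × r. If r = 0 the increase is 0. Increase in percentage points otherwise:

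| p | q | r = 25% | r = 50% | r = 100% |
|---|---|---|---|---|
| 40% | 5% | 0.75 | 1.5 | 3.0 |
| 40% | 15% | 2.25 | 4.5 | 9.0 |
| 40% | 30% | 4.5 | 9.0 | 18.0 |
| 60% | 5% | 0.5 | 1.0 | 2.0 |
| 60% | 15% | 1.5 | 3.0 | 6.0 |
| 60% | 30% | 3.0 | 6.0 | 12.0 |
| 80% | 5% | 0.25 | 0.5 | 1.0 |
| 80% | 15% | 0.75 | 1.5 | 3.0 |
| 80% | 30% | 1.5 | 3.0 | 6.0 |

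Smallest: 0.20 × 0.05 × 0.25 = 0.0025, or 0.25 points. Middle: 0.40 × 0.15 × 0.50 = 0.03, so 60% is reported as 63%. Largest: 0.60 × 0.30 × 1 = 0.18, so 40% is reported as 58%.

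For scale, the exact (Clopper-Pearson) 95% interval around 60% is 49.7–69.7% with 100 patients and 52.9–66.8% with 200, the planned enrolment limits. The middle case lies well inside that. The upper end of the grid is comparable to or larger than the half-width, and it is a one-directional shift that more patients would not reduce.

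**The case against.** The strongest reply is that a reader might infer that the primary endpoint necessarily counts treatment failures and benefits as drug-related harm. The documents do not support that. Entry depends on a suspected relationship, and nothing says that investigators will mark such reports as related; a dispensing error, for instance, need not be. This stands, and it is why the size is left open.

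Other tempting extensions also fail:

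- *Phase III non-response as the size of the problem.* Protocol Section 1 gives 26.3% and 14.6% responders, hence 73.7% and 85.4% non-responders. But a responder there needed normal mean UFC without up-titration, and this study also enrols patients already on the drug. Those figures are not a rate of lack-of-efficacy reports.
- *Loss of comparability with the pivotal trial's AE profile.* The documents do not give that trial's AE definition.
- *Proof that the SAP overlooked the list.* The SAP follows Section 6 of the "study protocol (as amended on 20SEP2013", before the list existed. That reference concerns Section 6 only, whereas the AE definition is in 3.5.2.1, and SAP versions 2.1 and 2.2 postdate Amendment 2. What can be said is that the current SAP contains no rule for these reports.

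It is also fair that the study is exploratory, that collecting these reports was a deliberate programme standard, and that reports coded to their own preferred term would leave the clinical rows unchanged. This limits the damage in the tables and rates by preferred term. It does not help the any-related-AE total, and that descriptive percentage is itself the primary result.

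**Conclusion.** The gap is real but conditional. By the protocol's own rule, reports without a clinical event, including benefit, are AEs, and no analysis section separates them. They count in the primary percentage when marked as suspected related. They count without that condition in the AE tables regardless of relationship and, above the display threshold, in the AE rates. The AE definition also differs before and after July 2016; how many patients fall in each period is not stated.

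The effect on the primary percentage is (1 − p) × q × r: zero if no such report is judged related, and 0.25 to 18 points for p = 40–80%, q = 5–30% and r = 25–100%. That range illustrates assumptions and is not an estimate for this study. Collecting these reports is not an error; the fault is a missing analysis rule. Separately, the word undesirable in the AE definition does not fit the listed "Unexpected beneficial effect".

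**What to change.** Leave data collection, safety reporting and the protocol-defined primary endpoint as they are. Narrowing the endpoint in the SAP alone would put it in conflict with Protocol 2.1.1, 3.5.2.1 and 6.4.1.

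In SAP 8.4.1 and 6.2.4:

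- Fix before database lock a list of preferred terms for the special scenarios. SAP 8.4.1 already works this way for AEs of special interest.
- Add a short medical review of flagged records, because a preferred term alone cannot show whether a clinical event occurred.
- Report special-scenario records without a clinical event in their own table and listing.
- Present the primary related-AE percentage, the overall AE incidence and the exposure-adjusted AE rates both with and without these records. The figures without them also largely remove the effect of the July 2016 change in definition.

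In Protocol 3.5.2.1, reconcile the requirement that an AE be undesirable with the inclusion of a beneficial effect.

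The cost is one list, one extra table with its listing, the with-and-without rows, and a short medical review. The analysis change needs nothing from the sites or the CRF.
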